1.2 Schema

1.3 Schedule of Activities (SoA) Cohort A & B

This study consists of screening, enrollment and randomization, treatment, and follow-up. Follow-up will include evaluation of the treatment and subsequent infection, re-infection, adverse events, and long-term sequelae of treatment and/or infection. The detailed schedule of study procedures and assessments with the time intervals is shown in Table 1.

Table 1

| Procedure | Screening & Enrollment | | Treatment / Placebo Phase | | | | | Follow-up ^b | | |
|---|------------------------|----------------------------|---------------------------|-------|--------------------|-------|-------|------------------------|-------------------------------|----------------------|
| | Screening ^a | Enrollment / Randomization | Day 1 | Day 2 | Day 3 ^f | Day 4 | Day 5 | Day 14 (± 1 day) | Day 35 ^c (+3 days) | 12 Months (±30 days) |
| Informed Consent / HIPAA | X | | | | | | | | | |
| Inclusion/Exclusion | X | | | | | | | | | |
| Demographics | X | | | | | | | | | |
| Randomization | | X | | | | | | | | |
| Hydroxychloroquine / Placebo (Vitamin D with calcium) | | | X | X | X | X | X | | | |
| Patient Reported symptoms ^c | | | | | X | | X | X | X | |
| Adverse Event Assessment | | | | | X | | X | X | X | X |
| Outcomes ^d | | | | | | | | X | X | X |

a. Screening must be completed within 48 hours prior to study enrollment

b. Follow-up visits will consist of a phone call to the patient. Hydroxychloroquine and placebo patients will be followed.

c. Includes: patient reported temperature, cough, difficulty breathing, sore throat, chills, muscle pain, headache, new loss of taste or smell, and diarrhea.

d. Did the patient acquire COVID-19?

e. Day 35 should be at least 30 days (+3 days) post last dose of drug.

f. Day 3 and 5 AE assessment via phone call. (window ±1day)

2.0 Introduction

2.1 Study Rationale

Currently, prevention of person-to-person transmission of SARS-CoV-2, the virus which causes COVID-19, is achieved by reducing close contact through physical distancing measures and through the use of personal protective equipment (PPE) in the healthcare setting. The effect of post-exposure medication treatment on acquisition of infection or progression to symptomatic disease is unknown.

2.2 Background

Coronavirus Infectious Disease-2019 (COVID-19) is an infection caused by a novel virus, Severe Acute Respiratory Syndrome Coronavirus 2 (SARS-CoV-2), which emerged in the winter of 2019 initially in China, then spread to involve the entire world in a pandemic. Infected individuals may be asymptomatic, while others demonstrate a range of symptoms from upper respiratory symptoms to pneumonia, respiratory failure, acute respiratory distress syndrome, or death.

Hydroxychloroquine inhibits SARS-CoV-2 replication in vitro and may have antiviral effects in people with COVID-19 disease (Yao *et al.* 2020). It is postulated that early preemptive therapy may prevent disease or reduce severity, but its effectiveness in the post-exposure setting is unknown.

3.0 Objectives and Endpoints

3.1 Primary Objectives

- Cohort A: Determine whether post-exposure prophylaxis with hydroxychloroquine can prevent COVID-19 in healthcare workers with direct patient contact who have been exposed to a known case of COVID-19.
- Cohort B: Determine whether post-exposure prophylaxis with hydroxychloroquine can prevent COVID-19 in high-risk individuals who have been exposed to a known case of COVID-19.

3.2 Primary Hypothesis:

- Cohort A: Primary Hypothesis: Hydroxychloroquine will reduce the number of healthcare workers that convert to infected status post-exposure compared with placebo.
- Cohort B: Primary Hypothesis: Hydroxychloroquine will reduce the number of high-risk individuals that convert to infected status post-exposure compared with placebo.

4.0 Study Design

4.1 Overall study design

This is a prospective, double-blind, randomized, placebo-controlled study in two distinct cohorts to evaluate the efficacy and safety of hydroxychloroquine in the prevention of COVID-19 infection. Additional sub-studies will be added and removed throughout this larger “tent” protocol to answer other objectives. These studies will be listed in the appendices of this protocol.

Other non-Sanford institutions will be allowed to participate in this study after all legal and regulatory documents are final.

Sanford Health will function as the lead site for trial oversight.

4.2 End of Study Definition

A participant is considered to have completed the study if he/she has completed all phases of the study including last follow up visit at 12 months.

5.0 Study Population

5.1 Inclusion Criteria

See Synopsis (section 1.1)

5.2 Exclusion

See Synopsis (section 1.1)

5.2 Screen Failures

Screen failures are defined as participants who consent to participate in the clinical study but are not subsequently enrolled. A minimal set of screen failure information is required to ensure transparent reporting of screen failure participants. Minimal information should include demography, screen failure details, eligibility criteria, and any serious adverse event (SAE). Screen failures will not count towards total enrollment.

6.0 Study Intervention

6.1 Study Intervention(s) Administered:

Hydroxychloroquine/placebo (vitamin D with calcium) will be administered as part of this study. Randomization will occur at a 1:1 ratio in each cohort. Participation in additional non-interventional clinical research studies is allowed. If the participant becomes infected with COVID-19, the participant will stop the intervention and be treated per the discretion of their primary care provider.

Subjects enrolled will be assigned to the appropriate cohort and randomized to receive hydroxychloroquine 200mg tablets, Day 1 – 2 tablets by mouth twice per day, Day 2-5 1 tablet by mouth twice per day (total of 12 tablets) or placebo. Placebo will be vitamin D with calcium tablets 10mcg tablet - Day 1 – 2 tablets by mouth twice per day, Day 2-5 1 tablet by mouth twice per day (total of 12 tablets). Subjects will be monitored for any toxicities during and after treatment.

Table 2. Intervention dosing

| Drug | Dose | Dose Frequency | Route |
|--|-----------|-------------------------|-------|
| Hydroxychloroquine 200 mg tablets | 2 tablets | Twice daily on day 1 | PO |
| | 1 tablet | Twice daily on days 2-5 | PO |
| Placebo (vitamin D with calcium, 10mcg/25mg tablets) | 2 tablets | Twice daily on day 1 | PO |
| | 1 tablet | Twice daily on days 2-5 | PO |

6.2 Hydroxychloroquine Sulfate (See Appendix C for more information)

6.2.1. Other Names

IUPAC: 2-[4-[(7-chloroquinolin-4-yl)amino]pentyl-ethylamino]ethanol

MeSH: Plaquenil; Hydroxychlorochin; Hydroxychloroquine;
Hydroxychloroquine Sulfate: Hydroxychloroquine Sulfate (1:1) Salt;
Oxychlorochin; Oxychloroquin; 4-aminoquinoline

6.2.2. Classification

Immunosuppressive, anti-inflammatory, anti-autophagy, and anti-malarial

6.2.3. Dose Specifics

One tablet of 200 mg of hydroxychloroquine sulfate is equivalent to 155 mg base. See section 6.1 for dosing.

6.2.5. Preparation

No special preparation.

6.2.6. Administration

Take hydroxychloroquine sulfate by mouth, preferably with a meal or a glass of milk.

6.2.7. Contraindications

Use of hydroxychloroquine sulfate is contraindicated in patients with known hypersensitivity to 4-aminoquinoline compounds. Use with

caution in patients with alcoholism, hepatic/renal dysfunction, glucose-6-phosphate dehydrogenase (G-6-PD) deficiency, gastrointestinal, neurological, or blood disorders. A dose reduction may be required.

6.2.8. Availability

Commercially available as a tablet for oral administration. For the purposes of this study the tablet drug will be provided by Sanford Research and supplied in 200mg tablets with matching placebo.

6.2.9. Side Effects

1. Ocular:

It is recommended that hydroxychloroquine be discontinued if ocular toxicity is suspected and the patient should be closely observed given that retinal changes (and visual disturbances) may progress even after cessation of therapy.

Retinal toxicity from hydroxychloroquine is serious but very rare. The incidence rises sharply to about 1% at 5 years of use, so the American Academy of Ophthalmology recommends screening starting after 5 years. Toxicity is more common with doses exceeding 400 mg/day or a total dose of more than 1000 g. This study dose is 800 mg for 1 day then 400 mg for 4 more days (Marmor *et al.* 2011).

2. Cardiac: Post marketing cases of life-threatening and fatal cardiomyopathy have been reported with use of hydroxychloroquine sulfate. Patients may present with atrioventricular block, pulmonary hypertension, and sick sinus syndrome or with cardiac complications. Electrocardiogram (ECG) findings may include atrioventricular, right or left bundle branch block. Signs or symptoms of cardiac compromise have appeared during acute and chronic treatment. Clinical monitoring for signs and symptoms of cardiomyopathy is advised. Chronic toxicity should be considered when conduction disorders (bundle branch block/atrio-ventricular heart block) or biventricular hypertrophy are diagnosed. If cardiotoxicity is suspected, prompt discontinuation of hydroxychloroquine sulfate may prevent life-threatening complications.

Hydroxychloroquine sulfate prolongs the QT interval. Ventricular arrhythmias and torsades de pointes have been reported in patients taking hydroxychloroquine. Therefore, hydroxychloroquine sulfate should not be administered with other drugs that have the potential to prolong the QT interval.

Hydroxychloroquine has been used for decades for malaria and autoimmune disease without pre-treatment EKGs or routine cardiac monitoring. A 2018 review of short-term antimalarial treatment including chloroquine, which is known to carry greater risk of toxicity, found no serious cardiac adverse events among participants (n=1076), receiving acute therapy for malaria. With chronic use of hydroxychloroquine (years), QT prolongation and cardiomyopathy have occurred. This study uses a 5-day course and subjects with heart disease will be excluded (Haeusler et al. 2018).

3. Worsening of Psoriasis and Porphyrria: Use of hydroxychloroquine sulfate in patients with psoriasis may precipitate a severe attack of psoriasis. When used in patients with porphyria the condition may be exacerbated. The preparation should not be used in these conditions unless in the judgment of the physician the benefit to the patient outweighs the possible hazard.
4. Proximal Myopathy and Neuropathy: Skeletal muscle myopathy or neuropathy leading to progressive weakness and atrophy of proximal muscle groups, depressed tendon reflexes, and abnormal nerve conduction, have been reported. Muscle and nerve biopsies have been associated with curvilinear bodies and muscle fiber atrophy with vacuolar changes. Assess muscle strength and deep tendon reflexes periodically in patients on long-term therapy with hydroxychloroquine sulfate.
5. Neuropsychiatric Events, Including Suicidality: Suicidal behavior has been rarely reported in patients treated with hydroxychloroquine sulfate.
6. Hypoglycemia: Hydroxychloroquine sulfate has been shown to cause severe hypoglycemia including loss of consciousness that could be life threatening in patients treated with or without antidiabetic medications. Patients treated with hydroxychloroquine sulfate should be warned about the risk of hypoglycemia and the associated clinical signs and symptoms. Patients presenting with clinical symptoms suggestive of hypoglycemia during treatment with hydroxychloroquine sulfate should have their blood glucose checked and treatment reviewed as necessary.
7. Dermatologic Effects: Dermatologic reactions to hydroxychloroquine sulfate may occur and, therefore, proper care should be exercised when it is administered to any patient receiving a drug with a significant tendency to produce dermatitis.

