| | 
 • High-risk person defined by: 
 • Age 18-44 with 2 or more comorbidities listed below • Age 45-79 with any comorbid condition listed below • Age 80 and above (regardless of comorbid conditions) • Co-morbid list 
 ○ Congestive Heart Failure (CHF) ○ Chronic lung disease[‡] ○ Solid organ transplant or immunosuppression* ○ Chronic Kidney Disease or End Stage Renal Disease ○ Diabetes mellitus ○ Cardiovascular disease/Hypertension ○ Smoking/Vaping (currently using or history of using in the past 1 year) ○ Obesity (calculated by height and weight per participant report) ○ Hyperlipidemia ‡Includes any of the following: asthma, chronic obstructive pulmonary disease, emphysema * Defined as an outpatient prescription of greater than 10 mg/day of prednisone or equivalent, use of chemotherapy, or use of immunosuppressive agents for solid organ transplant or for an autoimmune disease. • No current symptoms attributable to COVID-19 • No prior COVID-19 positive diagnosis (eligible if previous testing is negative and meets all other inclusion and exclusion) • Ability to provide informed consent • Confirmed review of concomitant medications (with emphasis on cardiac medications) |
| | 
Exclusion Criteria:
 
Exclusion Criteria Cohort A & B:
 
 • Known allergy to hydroxychloroquine or quinine • Known history of long QT syndrome • Known history of arrhythmia or dysrhythmia • Known current QTc >500 ms • Known G6PD deficiency • Known history of hypoglycemia • Pregnant or Nursing by patient history • Use of any of the following concomitant medications: See Appendix D for Exclusion medication list • Concurrent diagnosis of dermatitis, porphyria, or psoriasis • History of chronic liver disease, including cirrhosis and/or diagnosis of hepatitis (infectious, idiopathic, or immune) • History of chronic kidney disease • Pre-existing retinopathy • Already taking hydroxychloroquine • Any condition or medication in the opinion of the investigator that would prohibit the use of hydroxychloroquine • Enrollment in another clinical with investigational drug or device • Inability to swallow pills • Adults unable to provide informed consent |

| | |
|---------------------------|--|
| | |
| Sample Size | Cohort A n= 1356 Cohort B n= 383 |
| Study Intervention | Hydroxychloroquine vs. Placebo (Vitamin D with calcium) |

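### Section 6.2.9 says people with heart disease are excluded, but the eligibility criteria do not exclude them and count heart failure and cardiovascular disease towards Cohort B entry

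*Combined protocol and SAP*

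**What the plan says.** Section 6.2.9 (Side Effects, cardiac item) describes fatal cardiomyopathy, QT prolongation and torsades de pointes with hydroxychloroquine. It then gives reasons for reassurance: long use without pre-treatment ECGs, a review of short-term antimalarial treatment (n=1076), the short course, and an exclusion. The last two come in one sentence: "This study uses a 5-day course and subjects with heart disease will be excluded".

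Sections 5.1 and 5.2 contain no criteria of their own and send the reader to the synopsis. There, the exclusions shared by Cohorts A and B include "Known history of long QT syndrome", a known arrhythmia or dysrhythmia, and a known current QTc above 500 ms. Heart failure, ischaemic disease and structural disease are not named.

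The Cohort B high-risk definition uses a comorbidity list that begins with CHF and also contains "Cardiovascular disease/Hypertension". The list operates through age: "Age 18-44 with 2 or more comorbidities listed below" or "Age 45-79 with any comorbid condition listed below". From age 80, entry does not depend on comorbidity.

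Section 6.3.8 names heart disease and arteriosclerosis among the contraindications to the vitamin D with calcium comparator.

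**The concern.** The protocol offers the exclusion of heart disease as one of its cardiac protections, but the criteria do not deliver it. Followed as written, they allow a person with CHF to be randomised to hydroxychloroquine, and in Cohort B the CHF itself can be the reason that person qualifies. An IRB reading section 6.2.9 would credit the trial with a safeguard that does not operate.

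The safeguard matters because it would act before dosing. The schedule in section 1.3 has no ECG; that is the sponsor's stated choice and is not contested here. The adverse event calls on Days 3 and 5, the enrolment hold in section 8.3.1, and the weekly review and committee meetings in section 8.3.3 all act after treatment has begun.

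**Working it through.** The plan gives no figure to reproduce. The check sets section 6.2.9 against every provision that could carry it out.

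**1. Shared exclusions (section 1.1).** There are 17. Three are cardiac: long QT syndrome, arrhythmia or dysrhythmia, known QTc above 500 ms. They cover rhythm and repolarisation disorders. Of the 17, the number excluding heart disease as a category is 0.

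**2. Cohort B comorbidity list (section 1.1).** There are 9 entries: CHF; chronic lung disease; transplant or immunosuppression; chronic kidney disease or end-stage renal disease; diabetes; cardiovascular disease or hypertension; smoking or vaping; obesity; hyperlipidemia. One (CHF) is wholly heart disease, and one (cardiovascular disease or hypertension) is partly so.

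**3. Routes into Cohort B for a person with CHF.**

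| Age | Requirement | Does CHF admit? |
|---|---|---|
| 18-44 | two listed conditions | yes, with one other |
| 45-79 | one listed condition | yes, alone |
| 80 and above | none | entry does not depend on it |

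A person with CHF can enter by all 3 of 3 routes, unless another exclusion applies. Cohort A has no comorbidity criterion, so heart disease neither qualifies nor excludes there.

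**4. Other provisions that might implement the statement.**

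- *Appendix D.* It excludes by drug, not diagnosis. Someone with CHF who takes digoxin, a loop diuretic, a thiazide or a listed QT-prolonging drug is out. Someone with CHF or coronary disease who takes none of the listed drugs stays eligible.
- *Cardiac-medication review (Cohort B inclusion).* It also concerns drugs. It checks what is taken and does not make heart disease disqualifying.
- *Investigator-opinion exclusion.* It is discretionary and does not name heart disease. The same synopsis lists CHF as qualifying, which gives an investigator little reason to use it for that diagnosis.
- *Medical history and licensed review (sections 8.1.1, 8.1.3 and 8.1.5).* These confirm the criteria as written, and under those criteria CHF counts towards entry.

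None of the four makes the statement in section 6.2.9 true.

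**5. Size.** Cohort B plans 383 participants at 1:1, so 383 / 2 = 191.5, or about 191 to 192 on hydroxychloroquine. That is the size of the arm, not the number with heart disease. The documents give no prevalence of heart disease, so the number affected cannot be computed.

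**The case against.** The strongest reply is that section 6.2.9 is the stray text. It is a narrative remark in a side-effects section, whereas the criteria put CHF first on the Cohort B list, add cardiovascular disease, and ask for a medication review with a cardiac emphasis. Together these suggest that the sponsor may have meant to enrol cardiac patients and control risk through their drugs. The hydroxychloroquine label text in Appendix C does not name heart failure as a contraindication. This part of the reply stands: correcting section 6.2.9 is a legitimate resolution if that was the intent. It does not remove the conflict, and it leaves the comparator's heart-disease contraindication in section 6.3.8 to be explained.

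A second reply is that heart disease is undefined and could be shorthand for the three rhythm exclusions, since the sentence cites a review of arrhythmogenic toxicity. The same section discusses cardiomyopathy, however, and CHF is heart disease on any ordinary reading. What stands is that any list of diagnoses beyond the bare term is an interpretation, so the sponsor must define it.

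A reader might also infer more than the documents support:

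- That all 1,739 planned participants (1,356 + 383) are exposed to the problem. That figure only counts the people to whom the shared exclusions apply. CHF is a qualifying condition in Cohort B alone.
- That the criteria are certainly the wrong text, so that rewording section 6.2.9 could never be enough. The documents do not settle which text reflects the intent.
- That sites will certainly enrol such patients. Section 8.1.5 refers to an inclusion/exclusion source document that is not reproduced, so its content cannot be checked.

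**Conclusion.** The conflict is real and lies in the current text. The protocol claims a cardiac safety exclusion that its only stated criteria do not contain, and for Cohort B those criteria run the other way. It needs an amendment, because the sentence supports the cardiac risk assessment and the other provisions only narrow the gap.

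The standard applied is the protocol's own commitment in section 6.2.9, supported by its own comparator contraindication in section 6.3.8. No outside standard is used, and no claim is made that hydroxychloroquine is contraindicated in heart failure. The conclusion assumes that the synopsis is the complete set of criteria, as sections 5.1 and 5.2 state, and that heart disease includes heart failure. How many of the 383 planned Cohort B participants would be affected is unknown.

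**What to change.** **Preferred, because it follows the protocol's own words in sections 6.2.9 and 6.3.8:**

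1. Add known heart disease to the exclusions for Cohorts A and B. The sponsor should define the term, for example as heart failure, ischaemic heart disease, cardiomyopathy or other structural disease. This is the essential step, because Cohort A and the age-80 route do not use the comorbidity list.
2. Delete CHF from the Cohort B list.
3. Reduce the cardiovascular disease entry to hypertension alone. Keeping non-cardiac vascular disease as a qualifying condition would still clash with the arteriosclerosis contraindication in section 6.3.8.
4. Update the screening form to match.

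**Cost.** This is an amendment to wording and a form, with no new procedure. The Cohort B pool shrinks by an amount the documents do not allow to be computed, and results would not apply to people with heart disease. The list would go from 9 entries to 8. Kidney disease is already overridden by its own exclusion, so 7 usable entries remain, plus the age-80 route; Appendix D already narrows some of these. The sponsor should also check that the 30% control-arm conversion rate in section 9.2, on which the 383 rests, still suits the narrower cohort.

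**Alternative, if the sponsor did intend to enrol people with heart disease:** remove the statement from section 6.2.9, set out the actual cardiac exclusions there, justify the exposure to the IRB, and resolve the comparator's heart-disease contraindication in section 6.3.8. This keeps the recruitment pool but withdraws a stated protection.

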6.3 Vitamin D with calcium (Cholecalciferol)

6.3.1 Other Names IUPAC Name: (1S,3Z)-3-[(2E)-2-[(1R,3aS,7aR)-7a-methyl-1-[(2R)-6-methylheptan-2-yl]-2,3,3a,5,6,7-hexahydro-1H-inden-4-ylidene]ethylidene]-4-methylidenecyclohexan-1-ol

MeSH: (3 beta,5Z,7E)-9,10-Secosterolesta-5,7,10(19)-trien-3-ol;
Calcitol; Cholecalciferol; Vitamin D3

6.3.2 Classification Lipophilic secosteroid

6.3.3 Mode of Action

Vitamin D with calcium is dietary supplement used to promote calcium absorption in intestines, bone resorption, increase phosphate levels to maintain skeletal calcium balance. *In vivo* synthesis of the major biologically active metabolites of vitamin D with calcium occurs in two steps. First, in the liver microsomal enzymes convert vitamin D to calcifediol (25-hydroxycholecalciferol). Second, calcifediol is released into systemic circulation where it binds vitamin D-binding protein, an α -globulin carrier protein that transports it to the proximal tubules of the kidneys where Parathyroid hormone regulates its further hydroxylation to calcitriol (1,25-dihydroxycholecalciferol). Calcitriol is again released into systemic circulation, binds to vitamin D-binding protein and is distributed to throughout the body including to target organs like intestine, kidney, and bone. Vitamin D is indicated in treatment of hypoparathyroidism, refractory rickets, and familial hypophosphatemia.

Vitamin D3 and vitamin D2 are bioequivalent.

